# **Alternatives to Participation**

This study does not involve medical diagnostics or treatments for which alternatives should be offered.

A series of signal acquisition and processing software will be developed to collect and analyze sEMG and IMU signals from wearable sensors to develop algorithms for person-centric AAC cursor control, which will then serve to train machine learning algorithms to achieve an individualized AAC keyboard interface. We will validate these developments to show that an individualized keyboard interface can provide improved communication performance compared to a generic (QWERTY) keyboard interface.

The analyses of sEMG and IMU data will be guided by our knowledge of sensor and signal processing solutions for human machine interfaces for preliminary prototype studies and early development of concepts rather than to prove efficacy. We purposely want to collect data from a diverse group to be able to capture a range of movement limitations so that we have a variety of potential "adaptations" the interface can make. A *single-subject design approach will therefore be adopted to evaluate these different, personalized adaptations.* For this reason, data analysis will be conducted across participants to compare individualized AAC device performance to generic (QWERTY) AAC device performance.

Data analysis will follow the U.S. Department of Education standards for single-subject statistical designs as each participant engages in a series of transcription (scripted) tasks to examine user-specific communication performance between our individualized AAC device and a generic (QWERTY) AAC device. Participant communication performance will collected within a single session for each device; the QWERTY keyboard will be analyzed in the second session (Day 2) to serve as a reference for communication performance (i.e., due to widespread familiarity in using the QWERTY keyboard for mobile device communication) once participants are familiar with the sEMG/IMU access method.

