The change in level (mean) and variability (standard deviation) of communication performance will be evaluated via metrics of information transfer rate (bits/min), movement time (sec), target selection accuracy (%), movement variability (unitless), and perceived usability for each participant across the two conditions. Average level and variability metrics will be reported for each metric to understand the effects of using an individualized keyboard interface compared to a generic one.

The output of these tasks will be a novel body-worn sensor-based access method, an access assessment test protocol and individualized keyboard interfaces that provide more accurate and accessible AAC over generic interfaces for individuals with SPI.

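### QWERTY is always scored on Day 2 and each keyboard gets one session, so the comparison mixes keyboard with session; on the plan's one stated mechanism the mix favours QWERTY

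*Combined protocol and SAP*

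**What the plan says.** The data-analysis text stands under Alternatives to Participation in the combined protocol and SAP. It sets the schedule in one sentence: "Participant communication performance will collected within a single session for each device", and "the QWERTY keyboard will be analyzed in the second session (Day 2) to serve as a reference for communication performance". Two reasons are given. QWERTY is a suitable reference "due to widespread familiarity in using the QWERTY keyboard for mobile device communication", and it is scored "once participants are familiar with the sEMG/IMU access method".

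The closing paragraphs compare the mean and the standard deviation of five performance measures between the two conditions for each participant, then report averages, "to understand the effects of using an individualized keyboard interface compared to a generic one". The framework is named: "Data analysis will follow the U.S. Department of Education standards for single-subject statistical designs". The aim is put as "We will validate these developments to show that an individualized keyboard interface can provide improved communication performance", although the same text describes the work as "preliminary prototype studies and early development of concepts rather than to prove efficacy".

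The session for the individualized keyboard is not named. The available text describes no randomized or counterbalanced order, no repeat session for either keyboard, no practice criterion before scoring and no session term in the analysis.

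**The concern.** If every participant uses one keyboard on Day 1 and the other on Day 2, anything that changes between the days is part of the keyboard difference. More participants or more trials in the same order do not help, and no later analysis can recover the separation.

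The plan itself expects one such change, because it waits until participants know the access method before scoring QWERTY. If the individualized keyboard is scored while that skill is still being acquired, its mean may be lower and its SD higher for reasons unrelated to the layout. Both are planned outcomes. This is the only keyboard comparison in the available text, so a useful layout could look no better than QWERTY, or worse, and the data could not say why.

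**Working it through.** **Inputs.** From the data-analysis text: one session per keyboard, QWERTY in session 2, a within-participant contrast of means and SDs. Inferred: individualized keyboard in session 1. The available text gives no effect size, learning rate, between-day change or sample size, so there is no figure of the plan's own to reproduce.

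**Step 1: what the contrast estimates.** Write a participant's expected score as a + τ·(individualized) + π·(Day 2). Here τ is the keyboard effect and π is any Day 1 to Day 2 change not due to the keyboard.

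- Individualized, Day 1: a + τ
- QWERTY, Day 2: a + π
- Difference: τ − π

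If the individualized keyboard were instead scored in a later session than QWERTY, the difference would be τ + π: still confounded, with the sign of the bias reversed.

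**Step 2: can τ and π be separated?** This was checked by the rank of the design matrix, with illustrative numbers of participants, trials and sessions.

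| Design | Parameters | Rank |
|---|---|---|
| One participant, planned order | 3 | 2 |
| 10 participants, 20 trials per session, planned order | 12 | 11 |
| Same 10, five in each order | 12 | 12 |
| One participant, six alternating sessions, linear trend | 3 | 3 |

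The planned order is one short of full rank whether there is one participant or ten.

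**Step 3: what counterbalancing does.** Individualized first gives τ − π and QWERTY first gives τ + π. With equal numbers the average is [(τ − π) + (τ + π)]/2 = τ, if π is common and there is no carry-over. Each participant's own difference still contains −π or +π.

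**Step 4: direction on the stated mechanism.** On a measure where higher is better, growing familiarity makes π positive, so τ − π is below τ. With an assumed τ of 10 units:

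- π = 5: 10 − 5 = 5
- π = 10: 10 − 10 = 0
- π = 15: 10 − 15 = −5

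The first is a conservative positive result. The other two are a null and a negative result despite a real benefit. For movement time, where lower is better, the signs reverse.

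**Step 5: size, illustration only.** For a rate such as bits/min with no true keyboard effect, let the later session differ by an assumed proportion g. The apparent individualized effect is 1/(1+g) − 1.

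| g | Apparent effect |
|---|---|
| +5% | 1/1.05 − 1 = −4.8% |
| +10% | 1/1.10 − 1 = −9.1% |
| +20% | 1/1.20 − 1 = −16.7% |
| −5% | 1/0.95 − 1 = +5.3% |
| −10% | 1/0.90 − 1 = +11.1% |
| −20% | 1/0.80 − 1 = +25.0% |

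The positive-g rows correspond to the mechanism the plan states. The negative-g rows are shown for completeness and have little support in the documents.

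**The case against.** **The order works against the sponsor's own hypothesis.** This largely stands. Familiarity with the access method is the only session mechanism the plan states, and it favours QWERTY. A reader might infer that the schedule flatters the individualized keyboard, or that the direction of bias is wholly open. The documents support neither. The case for a worse Day 2 is thin: the Background remarks on readjustment concern existing access methods, position and environment have no fixed sign by day, and rest is planned at least every 10 minutes. But no between-day change is measured, so the net sign is not established, and conservatism does not help a null or negative result.

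**The order is deliberate and justified.** In part. Familiarity with QWERTY is a property of that keyboard and supports its use as the reference, not its position. Familiarity with the access method supports practice before scoring either keyboard. Some practice is probably built in already, since Specific Aims has the layout adapted from each participant's own movement data. That may shrink the practice effect, but no criterion is set.

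**Randomized order does not fit a single-subject design.** This stands as a limit on that remedy: it clears a common session effect from the group average only. Only alternation within participant protects the individual comparisons. Naming the single-subject standards does not itself alter the one-session schedule.

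**It is early development.** True, and it lowers the stakes. The stated aim is still to show that the individualized interface can improve performance.

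**The session counts contradict each other.** A reader might infer this from 1-2 sessions in the Protocol section and at least 3-4 in the SPI eligibility criteria. With a series of experiments planned, the first may apply per experiment and the second to the whole study. What remains is a clarification: a one-session option has no Day 2.

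**Conclusion.** The concern holds as a design weakness that is cheap to mend. With the individualized keyboard on Day 1, the planned difference estimates τ − π and cannot be attributed to the keyboard alone, in the mean or in the SD. Confidence in that confounding is high. It rests on the one-session-per-device schedule, which is stated, and on the Day 1 placement, which is inferred.

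On the stated mechanism a positive result would be conservative and a null or negative one uninterpretable. The net bias cannot be determined and its size is unknown; every percentage above comes from an assumed session change. Since the work is not meant to prove efficacy, this is a matter of design and reporting and does not invalidate the study.

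**What to change.** 1. Complete familiarization with the access method and construction of the individualized layout before either keyboard is scored.
2. Randomize keyboard order in equal numbers within SPI participants and within controls, and report results by order. State that this removes a common session effect from the group average only, and removes neither carry-over nor the session effect in single-participant comparisons.
3. Where stamina allows, alternate the keyboards in randomized blocks within participant, so that the single-participant comparisons are protected too.
4. If the fixed order is kept, report that keyboard and session are confounded and that practice favours QWERTY. Do not present the difference as the keyboard effect alone, and do not read a null or negative result as absence of benefit.
5. As a clarification, name the session in which each keyboard is scored and say how the one-session option fits with a Day 2.

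**Cost.** No extra participants. Items 1 and 2 need a randomization list and a preparatory step. If that step takes one visit, 1 + 2 scored sessions = 3, within the 3-4 asked of SPI participants, provided those visits are not already committed to other aims. No such criterion is listed for controls. Item 3 costs more: setup, rest and questionnaire times are not given, so the number of feasible blocks cannot be computed, and short blocks give a novel layout less sustained use. Items 4 and 5 need only text.
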